8.3 Demographic and Other Baseline Characteristics

All baseline summaries will be based on the safety population.

Frequency distributions and summary statistics for demographic and baseline variables will be presented across all subjects. Key demographic and baseline characteristics to be summarized include: age, birth gender, race, ethnicity, height, weight, BMI, highest level of education, alcohol history, recreational drug use history, smoking history, MMSE, CBB (if the CBB assessment is repeated, this second CBB score will be used in the CBB summary table), and ApoE Genetic testing.

All demographic and baseline characteristics data will be presented in listings.

8.4 Relevant Family History

Data from Family History CRF will be summarized in a listing.

8.5 Disease History

Months since symptom onset and diagnosis will be presented in a listing for the safety population.

8.6 Pregnancy Test

Data from Pregnancy Test CRF will be presented in a listing for the safety population.

8.7 Concomitant Therapy

A current version of the World Health Organization (WHO) Drug Dictionary will be used to classify medications by preferred term and WHO Anatomical Therapeutic Chemical (ATC) classification of ingredients. ATC classification level 3 will be used. If level 3 is missing, then level 2 will be used. If level 2 is missing, then level 1 will be used.

All concomitant medications data will be presented in listings for the safety population.

8.8 Medical and Surgical History

Medical and Surgical History will be coded using MedDRA Version 21.1. Medical and surgical history will be presented in a listing for the safety population.

8.9 Analysis of Efficacy Parameters

All efficacy information as well as related data (flortaucipir PET scan information and flortaucipir PET results) will be presented in the listings.

8.9.1 Qualitative Assessment of Images

The visual read results will be categorized as τ AD+, τ AD++ and τ AD-. The visual read results will be summarized by frequency distribution (count and percentage) for the efficacy population by subject eligibility and overall.

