7.3. Protocol for Image Collection

An imaging manual will be created for the flortaucipir F 18 PET scan procedures and distributed to participating imaging centers prior to site initiation.

Required scan data sets and transmission instructions will be provided to the PET centers for all scans acquired under this protocol.

PET scan images must be de-identified and assigned a unique patient number prior to submission to Avid.

Feedback regarding the flortaucipir F 18 scan will be provided to the investigator, inclusive of any incidental findings

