4 STUDY DESIGN

4.1 General Design

Study ¹⁸F-AV-1451-A24 is a multicenter screening study in subjects with early symptomatic AD (defined as prodromal AD and mild dementia due to AD).

All subjects will provide informed consent before starting any study procedures. This prescreening study targets subjects who are interested in participating in AD therapeutic clinical trials and have expressed a preliminary interest in a trial like the LMDC trial, and who are not known to have met any of the exclusion criteria for trials like LMDC based on medical history and clinical examination. However, consent for this protocol does not constitute consent for the LMDC trial or any other trials, and subjects who qualify for this protocol may still fail to qualify for trials like LMDC or other trials based on the results of this protocol or based on additional testing performed in those subsequent trials.

Screening assessments may take place over several days and will be performed within 30 days prior to flortaucipir F 18 injection. Screening assessments will include demographic information, cognitive testing, disease history, concomitant medications, vital signs, ECG and medical history. Subjects who are deemed eligible to continue will complete a flortaucipir PET scan.

A physician or a licensed/credentialed medial professional (i.e., a PET technologist, imaging center nurse or a regional equivalent) designated by the site principal investigator must assess or evaluate the subject prior to administration of flortaucipir F 18 injection to determine if they are still suitable to undergo the scan.

All subjects will receive a single IV bolus administration target dose of 370 MBq (10 mCi) of flortaucipir F 18 injection followed by saline flush. At approximately 75 minutes following injection, a continuous 30-minute brain scan will be performed.

The injection site will be observed for excessive inflammation or damage to the surrounding tissue at the injection site. Adverse events will be continuously monitored during the flortaucipir PET imaging visit. Subjects who experience an adverse event will not be discharged from the imaging center until the event has resolved or stabilized. A follow-up phone call to the subject, or informant where applicable, will be conducted within 2 or 3 business days of the imaging day, but not before 48 hours post-injection, to confirm subject well-being and to collect any new adverse events.

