A physician or a licensed/credentialed medial professional (i.e., a PET technologist, imaging center nurse or a regional equivalent) designated by the site principal investigator must assess or evaluate the subject prior to discharge from the imaging center to evaluate the subject's readiness for discharge.

Subjects who meet eligibility criteria will participate in this protocol until they complete their flortaucipir PET scan, or they discontinue, withdraw consent, or if the sponsor decides to end this protocol early.

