6.4.2 Quantitative assessment of images for Flortaucipir (SUVr based)

For the flortaucipir image, standard uptake value ratios (SUVr) will be calculated to estimate tau globally. SUVr will be calculated after the visual read and only on scans that

were $\tau\text{AD}+$ or $\tau\text{AD}++$. For global assessment, a target region derived statistically with a Multiblock Barycentric Discriminant Analysis (MUBADA) method will be used.

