7 STATISTICAL METHODS

7.1 General Methodology

All values will be summarized as a single group, early symptomatic AD. Frequency distributions including counts and percentages will be reported for all categorical outcomes. Summary statistics including number of subjects [N], mean, standard deviation [SD], median, quartiles, minimum and maximum values will be presented for all continuous outcomes.

All statistical analyses will be performed using SAS® version 9.3 or higher. Patient listings of all data from the eCRF as well as any derived variables will be presented.

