7.8 Examination of Subgroups

No subgroup analysis will be performed.

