8.9.2 Quantitative Assessment of Images

The Screening MUBADA SUV_r will be summarized using descriptive statistics [n, mean, SD, median, minimum and maximum values, and quartiles (25th and 75th percentile)] by visual read results (τ AD+, τ AD++), subject eligibility, and overall.

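### Does the undefined split of the imaging tables by subject eligibility, with the differing safety-population wording, require a change to the SAP?

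*SAP*

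**What the plan says.** The two imaging summary tables are specified in SAP 8.9. For the visual reads, 8.9.1 says: "The visual read results will be summarized by frequency distribution (count and percentage) for the efficacy population by subject eligibility and overall". For MUBADA SUVr, 8.9.2 asks for descriptive statistics by visual read (τAD+ and τAD++ only), "subject eligibility, and overall". Regional neocortical activity (8.9.3.1) is listed, not summarised.

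Two general statements sit beside these. SAP 7.1 says "All values will be summarized as a single group, early symptomatic AD", and SAP 7.8 says "No subgroup analysis will be performed".

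The documents speak of qualifying in more than one sense. SAP 4.1 uses it for entry to A24: "Subjects who meet eligibility criteria will participate in this protocol until they complete their flortaucipir PET scan". The same section says that subjects who qualify for A24 may still "fail to qualify for trials like LMDC or other trials based on the results of this protocol or based on additional testing" done in those later trials. Protocol 7.3 adds that "Feedback regarding the flortaucipir F 18 scan will be provided to the investigator", without saying whether that feedback contains an eligibility decision.

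On populations, protocol 8.1.1 limits the safety population to eligible patients who enrol and are dosed. SAP 8.1.2 has all subjects who enrol and are dosed. In both documents the efficacy population is built on the safety population. SAP 5.2 reports no departures from the protocol's planned analyses.

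**The concern.** A variable that splits every planned imaging summary should be traceable to a definition, a source and a set of levels. This one has none of the three in the text, and the candidate meanings would give different tables. Read literally, 7.1 and 7.8 leave no room for the split, so one programmer might print a single column and another two.

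It also seemed that one heading could cover different people in the two tables. A subject with a τAD- read who is classed as not eligible is counted in the read table but has no SUVr, so cannot appear in the SUVr table.

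At stake is the only planned summary by eligibility in a study whose primary objective is pre-screening. The word *eligible* in the protocol's safety population raised a second worry: whether a subject dosed despite failing an entry criterion counts in the safety tables, which serve the secondary objective, and in the imaging tables.

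**Working it through.** The plan gives no figure to reproduce. The check is mostly a comparison of texts.

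1. **Reach of the split.** Planned imaging summaries are 8.9.1 and 8.9.2, so 2; both carry the split. 8.9.3.1 is a listing.

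2. **Overall results.** Let n(r, e) be the number of efficacy-population subjects with read r and eligibility level e, unknown included. The overall count for read r is the sum of n(r, e) over e, whatever e means. Overall SUVr statistics use all scans with an SUVr and make no reference to e. Within a given efficacy population, the overall results are therefore identical under every reading.

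3. **The three readings.**

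| Reading | Content of the not-eligible column | What the documents say on source |
|---|---|---|
| Entry to A24 | Subjects dosed despite an entry deviation | Entry criteria in protocol 5.3 |
| Receiving trial's tau-imaging requirement, judged on the A24 scan | Subjects whose scan did not qualify | No criterion or field named |
| Final qualification for a receiving trial | Also those who failed later testing | No field named |

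 The third reading cannot be dismissed because the schedule in SAP 6.1 lacks such an item. That schedule is not an inventory of the eCRF: SAP 8.3 summarises ApoE and alcohol, recreational drug and smoking history, and none has its own row there. The fair statement for the second and third readings is that the source is not stated.

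4. **Sections 7.1 and 7.8 against 8.9.** Section 7.1 comes under general methodology and names a single diagnostic group. Section 8.9.2 also splits by visual read, so 7.1 cannot have been meant to bar every descriptive breakdown. Section 7.8 stands among standard items on covariates, multiplicity and active-control equivalence, and is naturally read as excluding formal subgroup analysis. The specific table instruction governs the table.

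5. **SUVr restriction.** SAP 6.4.2 states it: "SUVr will be calculated after the visual read and only on scans that" were read as τAD+ or τAD++. Section 8.9.2 names only those two read levels and prints n. The restriction applies equally to the overall column, so the eligibility split does not create it.

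6. **Safety population.** The documents give no rate of entry deviations. Assume 1% to 5% of 500 dosed subjects (500 is the approximate enrolment target, so full dosing is also an assumption):
 - 500 × 0.01 = 5 and 500 × 0.05 = 25 subjects differ between the two wordings.
 - The protocol population would be 500 − 5 = 495 down to 500 − 25 = 475.
 - For an event in one subject who belongs to both populations, 1/500 = 0.20% against 1/475 = 0.21% at the far end.

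 The planned tables are those of the SAP, so they use 500 throughout, and the same holds for the efficacy population built on it. SAP 8.1.1 defines enrolled by consent and data capture, which leaves no eligibility condition in the SAP's wording. Protocol 5.3.1 and 5.3.2 make the criteria a condition of enrolling, so *eligible* in protocol 8.1.1 may simply be redundant. Under SAP 8.10.2 every adverse event is listed.

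**The case for a change.** The strongest case for acting is that the gap is real and cheap to close. The term appears in no other section, the readings give different columns, and this is the one place where the SAP reports results by eligibility. A sentence of definition, a short exception in 7.1 and 7.8, and a line in 5.2 would remove all doubt.

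What stands: an outside reader cannot tell from these documents which eligibility is meant, the general wording of 7.1 and 7.8 does not acknowledge the breakdowns in 8.9, and SAP 5.2 does not mention the difference from protocol 8.1.1.

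What does not stand is that these gaps would lead to a wrong result. A programmer is unlikely to drop a breakdown ordered in both table specifications because of a general sentence elsewhere. The analysts work with the eCRF and image data, which the reader of these documents does not have, and would either find the eligibility field or ask for it. A definition drafted from outside would have to guess the sponsor's meaning. Extra labels and counts on the SUVr table would repeat a restriction already stated in 6.4.2. Amending the protocol's safety wording would bring it to the definition that the SAP already uses.

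**Conclusion.** No change to the plan is needed. The missing definition is a gap in detail that the sponsor's analysts would fill sensibly. The tension with 7.1 and 7.8 is one of wording, and the unrecorded difference in the safety population is a clerical matter with no effect on planned output.

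The reach is 2 of 2 imaging summary tables, in their eligibility columns only. Overall read counts, overall SUVr statistics and the SAP's safety tables do not change. The study has no hypothesis test and no power target; the target of about 500 rests on no statistical calculation, so no error rate or sample size is involved.

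This conclusion assumes that an eligibility field or decision exists in the study data, which the documents neither confirm nor exclude, and that the SAP definition of the safety population is the one applied. The 1% to 5% deviation rate only illustrates how far the two wordings could differ; the conclusion does not depend on it. When the results are read, the table's title or footnote should make clear which eligibility is shown.

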8.9.2 Quantitative Assessment of Images

The Screening MUBADA SUV_r will be summarized using descriptive statistics [n, mean, SD, median, minimum and maximum values, and quartiles (25th and 75th percentile)] by visual read results (τ AD+, τ AD++), subject eligibility, and overall.

8.9.3 Other Efficacy Variables

8.9.3.1 Increased Neocortical Activity

Increased neocortical flortaucipir activity by hemisphere and region will be presented in a listing.

8.10 Analysis of Safety

8.10.1 Extent of Exposure and Compliance to Study Treatment

The total dose administered (MBq) of Flortaucipir F 18 will be summarized using descriptive statistics. All exposure data captured on the CRF will be presented in listings for the safety population.

Because this is a study with only one bolus of study medication per imaging visit, compliance will not be summarized.

8.10.1.1 Unit Conversion and Volume Calculation

All exposure tables will display volume in MBq. Radioactive dose collected in millicuries (mCi) will be converted to MBq as follows:

$$MBq = 37 \times mCi$$

8.10.2 Adverse Events

TEAEs will be summarized by descending frequency, then alphabetically by SOC and preferred term. A subject will only be counted once per SOC and once per preferred term. Subject counts and percentages will be presented for the following summaries:

1. All TEAEs by system organ class (SOC) and preferred term;
2. All TEAEs by preferred term (in order of descending frequency);
3. All TEAEs by relationship to study drug, SOC, and preferred term;
4. All TEAEs by relationship to protocol procedure, SOC and preferred term;
5. All TEAEs by severity, SOC and preferred term
6. All Serious TEAEs by system organ class (SOC) and preferred term;
7. All TEAE leading to study termination by system organ class (SOC) and preferred term

For the summary of TEAEs by severity, if a subject has multiple events occurring in the same SOC or same preferred term, the event with the highest severity will be counted.

TEAEs by relationship to study drug and protocol procedure will be summarized as Related vs. Not Related. If a subject has multiple events occurring in the same SOC or same preferred term, the related event will be summarized.

All AE will be presented in the listings.

8.10.3 Vital Signs

All vital signs data will be presented in the listings.

8.10.4 Electrocardiogram (ECG)

All ECG data will be presented in the listings.

8.11 Pharmacodynamics

No pharmacodynamics analyses are planned for this study.

9 COMPUTER SOFTWARE

All analyses will be performed by Chiltern using SAS® Version 9.3 or later. All summary tables and data listings will be prepared utilizing SAS® software.

The standard operating procedures (SOPs) of Chiltern will be followed in the creation and quality control of all data displays and analyses.
